8.1.3 Overdose

An overdose is defined as the accidental or intentional administration of any dose of the product that is considered excessive and medically important as determined by the investigator. All occurrences of overdose (suspected or confirmed and irrespective of whether or not it involved rimegepant or placebo) must be communicated to Biohaven or a specified designee within 24 hours and be fully documented as an SAE. Details of any signs or symptoms and their management should be recorded including details of any antidote(s) administered.

8.1.4 Pregnancy

If following the baseline visit, it is subsequently discovered that a study subject, or the female partner of a male study subject, is pregnant or may have been pregnant at the time of the investigational product exposure, including during at least 6 half-lives after the product administration, the investigational product will be permanently discontinued in an appropriate manner (i.e., dose tapering if necessary for subject's safety). Protocol-required procedures for the study discontinued and the follow-up must be performed on the subject unless contraindicated by the pregnancy (i.e., x-ray studies). Other appropriate pregnancy follow-up procedures should be considered if indicated.

Sites should instruct subjects to contact the Investigator immediately if they become pregnant during the course of the study. The Investigator must immediately notify the Biohaven Medical Monitor (or designee) of the event and complete and forward the Pregnancy Report Form to the Pharmacovigilance CRO immediately via telephone within 24 hours and in accordance with SAE reporting procedures as described in Section 8.1.2.

Follow-up information regarding the course of the pregnancy, including perinatal and neonatal outcome and, where applicable offspring information must be reported on a Pregnancy Report Form.

Any pregnancy that occurs in a female partner of a male study subject should be reported to the sponsor. Information on this pregnancy will be collected on the Pregnancy Report Form, as appropriate.

8.1.5 Potential Drug Induced Liver Injury (DILI)

Wherever possible, timely confirmation of the initial liver-related laboratory abnormalities should occur prior to the reporting of a potential DILI event. All occurrences of potential DILIs, meeting the defined criteria, must be reported as SAEs as per Section 8.1.2.

Potential drug induced liver injury is defined as:

1. Aminotransferases (AT) (ALT or AST) elevation > 3 times the upper limit of normal (ULN)

AND

2. Total bilirubin (TBL) > 2 times ULN, without initial findings of cholestasis (elevated serum alkaline phosphatase)

AND

3. No other immediately apparent possible causes of AT elevation and hyperbilirubinemia, including but not limited to, viral hepatitis, pre-existing chronic or acute liver disease, or the administration of other drug(s) known to be hepatotoxic.

If any potential DILI is identified and meets the criteria above, the Biohaven Medical Monitor (or designee) should immediately be contacted for further instructions on appropriate follow up requirements.

8.2 Non-serious Adverse Events

A *non-serious adverse event* is an AE not classified as serious.

8.2.1 Collection and Reporting of Non-Serious Adverse Events

The collection of non-serious AE information should begin at the Baseline visit. Non-serious AE information should also be collected from any observational period intended to establish a baseline status for a subject.

Non-serious adverse events should be followed until conclusion or stabilization, or reported as SAEs if they become serious. Follow-up is also required for non-serious AEs that cause interruption or discontinuation of study drug or those that are present at the end of study treatment.

8.2.2 Laboratory Test Abnormalities

The following laboratory test abnormalities should be captured on the non-serious AE CRF page or SAE Report Form (paper or electronic) as appropriate:

- 1. Any laboratory test result that is clinically significant or meets the definition of an SAE;
- 2. Any laboratory abnormality that required the subject to have the study drug discontinued or interrupted;
- 3. Any laboratory abnormality that required the subject to receive specific corrective therapy.

9 STATISTICS

9.1 General Procedures

Categorical variables are tabulated with counts and percentages. Continuous variables are summarized with univariate statistics (e.g., n, mean, standard error, median, minimum and maximum).

For the calculation of descriptive statistics of observed data, subjects must have an initial value (e.g. baseline value) to be evaluable for endpoints based on values and changes from the initial value over time.

Tabulations of the following endpoints present the number of unique subjects with an event: protocol deviations; interruptions of study therapy; non-study medications; adverse events; and laboratory abnormalities. Thus, for these endpoints, multiple occurrences of the same event are counted only once per subject.

For the assessments of most endpoints, if a subject uses rescue medication before the endpoint data have been fully collected then the subject will be considered a failure on that endpoint. Full details will be provided in the statistical analysis plan.

9.2 Sample Size

If roughly 85% of the 715 subjects randomized to each treatment arm have a migraine in the allotted time period, there will be approximately 600 treated subjects per group.

Based on data from studies BHV3000-301 and BHV3000-302, 600 treated subjects provides 95% power to detect a difference between rimegepant and placebo on the subject's self-reported most bothersome symptom. Also, 600 subjects provides 95% power to detect a difference in freedom from pain at 2 hours. Having at 95% power on each co-primary endpoint provides roughly 90% power to detect a difference on both endpoints jointly.

For additional details, please see 15.4 Appendix IV – Power Calculations.

9.3 Populations for Analysis

- Enrolled subjects: Subjects who sign an informed consent form and are assigned a subject identification number.
- Randomized subjects: Enrolled subjects who receive a randomization treatment assignment from the IWRS (rimegepant or placebo).
- Treated subjects: Enrolled subjects who take study therapy (rimegepant or placebo).
- Modified Intent to Treat (mITT) subjects: randomized subjects that take study therapy, have a
 migraine of moderate or severe intensity at the time of treatment, and provide at least one posttreatment, efficacy data point.

No separate per protocol analysis set is defined for this study. There will not be any per protocol analysis conducted for this study.

9.4 Statistical Methods

9.4.1 Primary Endpoint(s)

BHV-3000 (rimegepant) is tested for superiority to placebo, at an alpha=0.05 level, on both the co-primary endpoints of pain freedom at 2 hours post-dose and freedom the most bothersome symptom at 2 hours post-dose.

Both endpoints are evaluated using Cochran-Mantel Haenszel methodology to estimate the common risk difference, and are stratified by the use of prophylactic migraine medication (yes or no) and country (China or Korea). These tests are conducted using the mITT subjects, with missing data at two hours imputed to be failure (i.e., Non-Completers = Failure; NC=F). Subjects that use rescue medication prior to reporting their co-primary endpoints will be classified as failures. Sensitivity analyses are described in the Statistical Analysis Plan (SAP).

9.4.2 Secondary Endpoint(s)

If the primary endpoint tests are both significant, then the key secondary endpoints are evaluated using the Hochberg procedure, conducted at alpha=0.05.

Like the co-primary endpoints, all of the key secondary endpoints are all binary endpoints. Hence the key secondary endpoints will be analyzed in the same manner as the primary endpoint. In particular they will be analyzed using Cochran-Mantel methodology to estimate the common risk difference, and are stratified by the use of prophylactic migraine medication (yes or no) and country (China or Korea).

9.4.3 Control of multiplicity

As discussed above, the co-primary endpoints are both tested at alpha=0.05. No correction for multiplicity is needed, since both co-primary endpoints must be positive for the study to be positive. The secondary endpoints are protected by a gate-keeper procedure. If both of the co-primary endpoints are significant, only then will the key secondary endpoints be tested for significance. Within the family of key secondary endpoints, multiplicity is controlled using the Hochberg procedure.

9.4.4 Missing Data

As discussed above, missing data for the co-primary endpoints is handled using a composite variable strategy, with missing data imputed to be failure (NC=F). In addition, subjects taking rescue medications prior to reporting their co-primary endpoints will be classified as failure.

The first two key secondary endpoints, pain relief at 2 hours post-dose and the ability to function normally at 2 hours post-dose, are binary endpoints and identical in structure to the co-primary endpoints. Hence, these two key secondary endpoints will be handled with the same composite variable strategy as is applied to the coprimary endpoints.

The third key secondary endpoint, use of rescue medications through 24 hours post-dose will be handled in a similar manner, with NC=F. However, since the use of rescue medications is the endpoint of interest, this is not treated as an intercurrent event.

The fourth and fifth key secondary endpoints, sustained pain freedom from 2 to 24 hours post dose, and from 2 to 48 hours post-dose, are with handled with a similar composite variable strategy. Subjects that use rescue medications before reporting the last data for an endpoint, either at 24 or 48 hours, will be classified as failures. Since subjects will need to sleep over periods as long as 24 or 48 hours, the requirement that non-completers be classified as failures is relaxed slightly. For these variables, subjects with more than 1 missing data point, other than at the critical 2, 24 or 48 hour data points, are classified as failures. For example, for sustained pain freedom from 2 to 24 hours, the subjects are expected to provide data at 2, 3, 4, 6, 8, and 24 hours. The data at 2 and 24 hour time points must be present or the subject is classified as a failure. However, any single data point may be missing at 3, 4, 6 or 8 hours without penalty. For sustained pain freedom from 2 to 48 hours, the data at 2, 24, and 48 hours are required to be present.

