7.6.2.4 Sustained Pain Freedom from 2 to 24 Hours

Sustained pain freedom is assessed using the number of mITT subjects that experienced no headache pain (response of 0 on Likert scale) at all time points from 2 through 24 hours post-dose. Subjects with missing pain scores at 1 or fewer time points, given that they have responses of no pain (response of 0 on 4-point Likert scale) at all other time points including the 2 and 24 hour post-dose time points, will be considered as successes. Subjects with responses missing at greater than 1 post-dose time point, missing data at the 2 or 24 hour time point (i.e. Non-Completers with more than 1 missing data point = Failure; NC1=F), or with any pain score greater than 0; or with any rescue medication within 24 hours (RM=F) will be considered as failures.

The proportion of mITT subjects who have a response of sustained pain freedom from 2 to 24 hours will be evaluated using the same methodology described in section [7.6.1.1](#).

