7.6.2.5 Sustained Pain Freedom from 2 to 48 Hours

Sustained pain freedom is assessed using the number of mITT subjects that experienced no headache pain (response of 0 on Likert scale) at all time points from 2 through 48 hours post-dose. Subjects with missing pain scores at no more than 1 time point, given that they have responses of no pain (response of 0 on Likert scale) at the 2, 24, and 48 hour time points will be considered as successes. Subjects with responses missing at greater than 1 time point; missing data at the 2, 24, or 48 hour time point (NC1=F); or with any pain score greater than 0; or with any rescue medication within 48 hours (RM=F) will be considered as failures.

The proportion of mITT subjects who have a response of sustained pain freedom from 2 to 48 hours will be evaluated using the same methodology described in section [7.6.1.1](#).

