7.6.3.3 Pain Relapse from 2 to 48 Hours

Pain relapse is assessed using the number of mITT subjects that are pain free at 2 hours post-dose as the denominator. The numerator is the number of these subjects that then have a relapse of pain at any severity (response of 1, 2, or 3 on the 4-point Likert scale) within 48 hours after administration of study medication. Subjects with more than 1 time point with missing data or with missing data at the 24, or 48 hour time point are classified as relapse.

If the subject becomes pain-free at 2 hours post dose and records the use of rescue medication, but no pain severity is recorded, it will be assumed that the medication is taken for relapse, and the subject will be counted as having experienced pain relapse.

The proportion of mITT subjects who have a response of pain relapse from 2 to 48 hours will be evaluated using the same methodology described in section [7.6.1.1](#).

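### The missing-data allowance for sleep forgives one reading between 3 and 8 h, so evening dosers who sleep through two or more count as sustained pain freedom failures and relapses without recorded pain

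*Protocol*

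**What the plan says.** Protocol 9.4.4 handles the co-primaries by counting missing data as failure. For key secondary endpoints 4 and 5 (sustained pain freedom 2–24 h and 2–48 h) it relaxes that rule slightly, and the reason it gives is "Since subjects will need to sleep over periods as long as 24 or 48 hours". The relaxation is that "any single data point may be missing at 3, 4, 6 or 8 hours without penalty". Beyond that, "subjects with more than 1 missing data point, other than at the critical 2, 24 or 48 hour data points, are classified as failures". The 2 and 24 h readings, and the 48 h reading for the longer endpoint, must always be present.

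The SAP carries this over as NC1=F. In 7.6.2.4, failures include "Subjects with responses missing at greater than 1 post-dose time point". In 7.6.2.5 they include "Subjects with responses missing at greater than 1 time point". Any rescue within the period is also failure.

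For pain relapse, SAP 7.6.3.3 uses "the number of mITT subjects that are pain free at 2 hours post-dose as the denominator". It then counts the following group as relapsed: "Subjects with more than 1 time point with missing data or with missing data at the 24, or 48 hour time point".

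Protocol 4.3.2.1 schedules diary readings at 15, 30, 45, 60 and 90 minutes and at 2, 3, 4, 6, 8, 24 and 48 h, and tells subjects to keep completing the diary for 48 h. Neither document has an asleep response, a sleep exemption or a wake-up rule.

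**The concern.** The allowance is justified by sleep, but between 2 and 24 h every scheduled reading falls at 3, 4, 6 or 8 h. A night that starts soon after the 2 h reading covers several of them, and only one is forgiven. Dosing is outpatient, at whatever hour an attack becomes moderate or severe, so evening dosing is ordinary use.

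Two sets of results are at stake. The sustained endpoints would depend partly on the clock time of dosing, and the reported durability of response would be too low. The relapse table would mix recorded return of pain with unanswered prompts, and nothing planned separates the two. A reader of the study report would take the relapse percentage as a clinical event rate.

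**Working it through.** **1. Reproduce the plan's own figure.** Inputs from Protocol Appendix IV: 600 evaluable per arm, Pearson chi-square, two-sided alpha 0.05. For 2 h pain freedom with placebo 14% and gain 8%, the calculation returns 95.1%, as stated there. That figure is not in dispute. The plan states no power for sustained pain freedom or relapse.

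**2. Which readings does a night cover?** This uses the diary schedule and assumes one unbroken sleep of 7 to 9 h during which prompts go unanswered.

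| Sleep begins (h after dose) | Readings missed | Count | Status under NC1=F |
|---|---|---|---|
| 2 to under 3 | 3, 4, 6, 8 h | 4 | failure |
| 3 to under 4 | 4, 6, 8 h | 3 | failure |
| 4 to under 6 | 6, 8 h | 2 | failure |
| 6 to under 8 | 8 h | 1 | allowed |
| 8 or later | none | 0 | allowed |

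With only 5 h of sleep, every bedtime from 2 to just under 6 h still loses at least two readings. A 15-minute window on each side moves the upper limit to 5.75 h; that is the only window size given (SAP 7.6.4.2, for the 8 h reading). The 24 and 48 h readings fall at the clock time of dosing, so a normal night does not remove them.

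**3. Clock-time example, sleep 23:00–07:00.**
- Dose 17:00: loses 8 h only and is allowed.
- Dose 18:00 or 19:00: loses 6 and 8 h and fails.
- Dose 20:00: loses 4, 6 and 8 h and fails. The 3 h reading falls exactly at bedtime, so a fourth loss is borderline.
- Dose just before 21:00: loses all four and fails.

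Take the 20:00 subject, pain-free at every recorded reading including 2, 24 and 48 h, with no rescue. This subject fails under SAP 7.6.2.4 and 7.6.2.5 and is a relapse under SAP 7.6.3.3.

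**4. Scale of m.** Let m be the share of otherwise sustained responders (for relapse, of 2 h pain-free subjects without a true relapse) who miss two or more of the four readings. The documents give no dosing-time distribution or night response rate. For orientation only: if doses were uniform over 07:00–21:00, sleep were 23:00–07:00 and nobody woke to answer, doses between 17:00 and 21:00 would be affected, which is 4/14 = 29%. Holding that dosing window and moving bedtime to 24:00 or 22:00 gives 3/14 = 21% or 5/14 = 36%. Waking to answer lowers all three. The range below is m = 15% to 30%.

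**5. Effect, with m equal in both arms.**

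Sustained rate reported = true rate × (1−m). The difference shrinks by the same factor.

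| True rates | m | Reported rates | Difference (points) | Power, 600 per arm |
|---|---|---|---|---|
| 14% vs 8% (assumed) | 0 | 14.0 vs 8.0 | 6.0 | 91% |
| | 15% | 11.9 vs 6.8 | 5.1 | 86% |
| | 30% | 9.8 vs 5.6 | 4.2 | 78% |
| 27.9% vs 7.4% (phase 2b, Protocol 1.3.2) | 0 | 27.9 vs 7.4 | 20.5 | >99% |
| | 15% | 23.7 vs 6.3 | 17.4 | >99% |
| | 30% | 19.5 vs 5.2 | 14.4 | >99% |

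Relapse reported = r + (1−r)m. For an assumed true r of 30%:
- m = 15%: 0.30 + 0.70 × 0.15 = 0.405, or 41%.
- m = 30%: 0.30 + 0.70 × 0.30 = 0.51, or 51%.

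The difference in relapse between arms also shrinks by (1−m).

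**The case against.** The strongest defence is that the protocol promises only a slight relaxation, and forgiving one gap is slight. The rule is disclosed, conservative, identical in both arms and in line with the composite strategy used elsewhere. How many gaps to forgive is partly a matter of judgement. This stands as a reason to keep the rule as primary. It does not explain why the stated reason is sleep when an ordinary night after evening dosing exceeds the allowance, nor why unanswered prompts should be reported as relapse.

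It can also be said that the problem would be partly visible. SAP 7.5.6 tabulates missing diary data (omitting the 3 h reading), SAP 7.6.1.1 tabulates observed pain levels with percent missing at each timepoint, and SAP 7.6.4.1 analyses pain freedom at 24 and 48 h separately. None of these reclassifies a sustained or relapse outcome. The last-observation-carried-forward and complete-case analyses are written for data missing at 2 h.

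A reader might infer that any dose within six hours of bedtime is affected. The schedule does not support that. Sleep starting before 2 h can remove the 2 h reading itself; missing that reading is already failure on the co-primary and puts the subject outside the relapse denominator. A reader might also infer that the sustained endpoints are likely to lose substantial power. That follows only under rates such as the assumed 14% vs 8%. At the documented phase 2b rates, which may be optimistic for this trial, power is not a problem.

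**Conclusion.** The point holds as a limited one. The allowance covers a night's sleep only when bedtime is about 6 h or more after dosing. For bedtimes about 2 to 6 h after dosing, a subject who sleeps 5 h or more without answering is failed on key secondary endpoints 4 and 5 and, if pain-free at 2 h, counted as a relapse, even with no pain or rescue recorded.

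The result is understated sustained response and overstated relapse: for m of 15–30%, a true 30% relapse rate reads as 41–51%, and the phase 2b difference of 20.5 points reads as 17.4–14.4. The size depends on m, on unbroken sleep and on equal missingness between arms, none of which the documents supply.

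A reader might go further and see a threat to the trial's main conclusion. The documents do not support that. The co-primaries need only the 2 h reading, and equal missingness dilutes a difference rather than creating one. Pain relapse is an other secondary endpoint outside the Hochberg family. What is affected is how far the durability and relapse estimates can be taken at face value.

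**What to change.** Keep NC1=F as the primary rule. Replacing it would depart from Protocol 9.4.4, and SAP 7.10 declares no changes from the protocol. Before unblinding, make two additions.

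1. In SAP 7.6.2.4, 7.6.2.5 and 7.6.3.3, add a pre-specified sensitivity analysis in which missing 3, 4, 6 or 8 h readings do not count as failure or relapse, provided that all recorded readings, including 2 and 24 h (and 48 h where relevant), are pain-free and no rescue was taken in the period.
2. In SAP 7.6.3.3, report by arm observed relapse (recorded pain or rescue use) separately from relapse imputed only because readings were missing.

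The cost is SAP wording and a few extra tables, with no new data. The drawback is that an overnight recurrence that was not recorded, not treated with rescue and gone by 24 h would count as sustained in the sensitivity analysis. With all four readings missing, the 22 hours from 2 to 24 h are unobserved. That is why it should stand beside the current rule and not replace it.

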9.4.5 Analysis of Safety

The investigators determine the intensity of AEs and the relationship of AEs to study therapy. The investigators' terms are coded and grouped by system organ class using the latest version of the Medical Dictionary for Regulatory Activities (MedDRA) available. AEs are presented by system organ class and preferred term, ordered by the overall frequency of events. If a subject had an adverse event with different intensities over time, then only the greatest intensity is reported.

Treatment Emergent AEs are tabulated in all treated subjects. SAEs occurring in subjects enrolled but not treated are listed. Deaths are listed for enrolled subjects without regard to onset.

The frequencies of the following safety events are summarized by treatment regimen, and overall, for treated subjects: SAEs; all AEs, non-serious AEs, AEs by intensity; and AEs by relatedness.

Graphical and tabular displays of liver function test results are provided.

Further safety analyses will be described in the statistical analysis plan.

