8 ADVERSE EVENTS

An Adverse Event (AE) is defined as any new untoward medical occurrence or worsening of a pre-existing medical condition in a subject or clinical investigation subject administered an investigational (medicinal) product and that does not necessarily have a causal relationship with this treatment. An AE can therefore be any unfavorable and unintended sign (including an abnormal laboratory finding for example) symptom, or disease temporally associated with the use of the investigational product, whether or not considered related to the investigational product.

Adverse events can be spontaneously reported or elicited during an open-ended questioning, examination, or evaluation of a subject. In order to prevent reporting bias, subjects should not be questioned regarding the specific occurrence of one or more AEs.

Subjects should be instructed to notify the Investigator when a Serious Adverse Event occurs.

There are two types of adverse events, Serious Adverse Events (SAE) and Non-Serious Adverse Events (AEs).

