7.7.2 Adverse Events

All Adverse Events (AEs) will be coded using the MedDRA version 23.0 or later. AEs toxicities will be graded according to National Cancer Institute Common Terminology Criteria for Adverse Events (NCI CTCAE), Version 5.0.

All AEs will be summarized for the following categories: AEs with onset prior to randomization, AEs with onset on or after randomization but prior to study treatment, and treatment emergent adverse events (TEAEs) with onset on or after study treatment respectively.

An overall summary of AEs, which includes the number and percentage of subjects reporting any AEs, AEs with onset prior to randomization, AEs with onset on or after randomization but prior to study treatment, serious AEs with onset prior to randomization, serious AEs with onset on or after randomization but prior to study treatment, TEAEs, drug-related TEAEs, TEAEs with CTCAE grade ≥ 3 , serious TEAEs, drug-related serious TEAEs, non-serious TEAEs, and TEAEs

leading to death will be presented. The number and percentage of subjects by SOC and PT will also be reported.

In the event of multiple occurrences of the same AEs being reported by the same subject, the maximum NCI-CTC Grade (Grade 5 > Grade 4 > Grade 3 > Grade 2 > Grade 1 > missing > not applicable) will be presented in the summary tables. A subject will be counted once at the highest grade for which the event occurred at the SOC level and the highest grade for each unique PT within that SOC level. Therefore, subjects may only contribute once to each PT and once to each SOC level. If CTCAE grade is missing for one event and the subject had no Grade ≥ 1 in the same category, “missing” row/column should be added in the summary tables with maximum CTCAE grade. The following summary tables will present the number and percentage of subjects by SOC, PT and maximum CTCAE grade.

- ◊ TEAEs
- ◊ Drug-related TEAEs

The following tables summarizing the number and percentage of subjects by SOC and PT will present only those TEAEs that occurred in at least 5% in at least one treatment group.

- ◊ TEAEs
- ◊ Drug-related TEAEs

All AEs will be included in listings. TEAEs are labelled in the listings. Listings will be provided for Serious Adverse Events (SAEs), AEs related to study drug, and grade >2 AEs separately. SAEs occurring in subjects enrolled but not treated will also be provided. AE leading to deaths will be listed for all enrolled subjects without regard to onset.

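### Treatment-emergent status rests on onset date alone, so an adverse event that starts before the dose and worsens or becomes serious after it can be counted as pre-treatment

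*Protocol*

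**What the plan says.** SAP 7.7.2 sorts AEs into three groups by onset. The first holds those that begin before randomization. The second is "AEs with onset on or after randomization but prior to study treatment". The third, which serves as the only TEAE definition in the SAP, reads "treatment emergent adverse events (TEAEs) with onset on or after study treatment respectively". The overall summary gives serious AEs the same split, with a row for "serious AEs with onset on or after randomization but prior to study treatment".

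Protocol 9.4.5 says that "Treatment Emergent AEs are tabulated in all treated subjects" but does not define the term, so the SAP wording is the only definition. SAP 7.4.1 decides whether an AE is on-treatment from its imputed start and stop dates. It names no date of worsening or of becoming serious.

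On changing events, Protocol 9.4.5 says: "If a subject had an adverse event with different intensities over time, then only the greatest intensity is reported". Protocol 8.2.1 says: "Non-serious adverse events should be followed until conclusion or stabilization, or reported as SAEs if they become serious". Protocol 8 defines an AE as "any new untoward medical occurrence or worsening of a pre-existing medical condition".

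**The concern.** An AE can be mild before the dose and become severe or serious after it. Aggravating something already present is one way a drug can do harm, and an onset-only rule has no place for it. The TEAE tables are the main between-arm safety display, and Protocol 10.2 provides for no data and safety monitoring committee. Few serious events are to be expected in a single-dose trial, so one event in the wrong row could change how the serious-TEAE line reads. A serious-AE row labelled as pre-dose would also be misleading if the seriousness was reached only after dosing.

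**Working it through.** The plan gives no figure to reproduce, and no alpha, power or sample size is involved. The check is a reading of the sections together, plus one ratio.

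**1. Can an AE be ongoing at dosing?** Yes. Non-serious AEs are collected from the Baseline visit (Protocol 8.2.1), the dose is held at home for up to 45 days (Protocol 4.3.2), and the end-of-treatment visit is within 7 (+2) days of dosing (Protocol 4.3.4). With the visit 7 days after the dose, the pre-dose share of post-randomization AE collection time is days to dose / (days to dose + 7):

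- dose on day 7: 7/(7 + 7) = 50%
- dose on day 20: 20/(20 + 7) = 74%
- dose on day 45: 45/(45 + 7) = 87%, or 45/(45 + 9) = 83% if the +2 days are used

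These are shares of calendar time. They show that the situation can arise, not how often it does.

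**2. Is a worsened AE the same event or a new one?**

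- Protocol 8.2.1 reclassifies a non-serious AE as serious if it becomes so, and mentions no new onset date.
- Protocol 8.1.2 handles an ongoing SAE that changes intensity by a follow-up report under the same event term.
- Protocol 9.4.5 allows one AE several intensities. That is a rule for tables, so it is only weak evidence on how records are kept.
- Protocol 8 counts "any new untoward medical occurrence or worsening of a pre-existing medical condition" as an AE, which could be read as calling for a new record.
- Protocol 6.1 lists eCRF instructions among the study materials. They were not supplied and may contain a rule.

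The first two items point to one continuing event. The last two leave room for a new record.

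**3. Where does the event go if it is kept as one?** Its onset is after randomization and before the dose. Under SAP 7.7.2 it therefore:

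- enters the pre-dose AE row and, once serious, the pre-dose serious-AE row
- is absent from the TEAE, serious TEAE, grade 3 or higher TEAE and drug-related TEAE counts, even if the investigator judges the worsening drug-related
- is absent from the tables by system organ class, preferred term and maximum grade, because those are specified for TEAEs and drug-related TEAEs only

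**4. Where does it remain visible?** In the any-AE row of the SAP summary, in the SAP listings (all AEs, SAEs, drug-related AEs, AEs above grade 2), and in the Protocol 9.4.5 frequencies of SAEs, all AEs, AEs by intensity and AEs by relatedness in treated subjects, which are not limited to TEAEs.

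**5. How many events?** The documents give no rate of AEs ongoing at dosing and none for later worsening. As a pure assumption, take about 600 treated subjects per arm, 2% to 10% with an AE ongoing at dosing, and 5% to 20% of those worsening:

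- low: 600 × 0.02 × 0.05 = 0.6 subjects per arm
- high: 600 × 0.10 × 0.20 = 12 subjects per arm

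The 20-fold range shows only that the number cannot be fixed from the documents.

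**The case against.** The strongest reply is that the consequence depends on record-keeping. If worsening of a condition present at dosing is an AE in its own right, as Protocol 8 can fairly be read, or if the eCRF instructions call for a new record, the worsening has a post-dose onset and the existing rule already makes it a TEAE. The SAP's maximum-grade rule, "In the event of multiple occurrences of the same AEs being reported by the same subject, the maximum NCI-CTC Grade", also presupposes that one subject may have several records. This stands as a limit on the point: the documents do not settle the matter. It does not remove the point. Protocol 8 does not say that its wording covers an AE already recorded in the study, and Protocol 8.1.2 and 8.2.1 lean towards updating the same event. With about 80 sites, classification would then depend on site habit.

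A second reply is that other analyses limit the harm, and this also stands. Liver injury, the AE of main interest in Protocol 1.2.4, is assessed from laboratory values under SAP 7.7.3 and 7.7.3.1, independently of the TEAE definition. Subjects with clinically significant findings at screening are largely kept out by Protocol 5.2.

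A reader might infer three stronger things that the documents do not support:

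- **The greatest-intensity sentence in Protocol 9.4.5 is the fault.** It is an ordinary tabulation rule. The gap is in the SAP 7.7.2 definition.
- **The pre-treatment category displays grades reached after dosing.** Its rows in the SAP summary are split by seriousness, not grade, so only seriousness can be misplaced there.
- **Events disappear from the report.** They remain in the outputs listed in step 4 of the working.

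**Conclusion.** The point holds in a limited form. As written, the onset-only rule puts an AE that begins between randomization and the dose, and worsens or becomes serious afterwards, outside every TEAE table. If it is serious, it appears in the pre-dose serious-AE row. This assumes that the AE is kept as one event with its original start date, which the SAE follow-up and upgrade rules suggest but do not state for every AE.

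The effect is misclassification between rows. Its size cannot be computed from the documents. It is probably small in a single-dose, double-blind trial, and matters most for serious events, where single cases count. The co-primary and other efficacy analyses are unaffected.

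**What to change.** In SAP 7.7.2, with a matching sentence in Protocol 9.4.5, define a TEAE as an AE that either starts on or after the study dose, or starts before the dose and increases in intensity or CTCAE grade, or becomes serious, on or after it.

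State how the change is dated: either a new record with its own start date, so that the pre-dose record keeps its pre-dose grade and seriousness, or a recorded date of worsening on the existing record. Put the same instruction in the eCRF instructions so that all sites follow one rule. Apply the definition to the overall summary, including its serious-AE rows, and to all TEAE tables.

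The cost is a few lines of text in each document. TEAE counts may rise slightly in both arms, and sites may enter a few more records.
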